### ***Secondary Outcomes***

Aim 3 is focused on Healthcare utilization: Cornell Services Index; Aim 4 addresses Caregiver burden: Bakas Caregiving Outcomes Scale, Zarit Burden Interview, SF-12, and PROMIS Satisfaction with Social Roles and Activities and assessment of Time Spent Caregiving. Program process evaluation will include process variables: e.g., rate of call completion, number of additional calls needed, call duration and calls initiated by the patient/caregiver.

Cornell Services Index: The Cornell Service Index is a widely used measure of healthcare services utilization, and will include number of hospitalizations and days hospitalized, number of emergency department visits, as well as number and type of clinic visits (both routine and those that address medical complications). It has been used in a number of TBI studies. The instrument allows one to modify it as needed, including specifically asking if a patient saw a provider for issues related to TBI. We will also modify it to include assessment of TBI-specific care, since our stakeholders were particularly interested in whether RTP improves the ability to access and follow through with care.

Bakas Caregiving Outcomes Scale: Since there are no TBI-specific caregiver quality of life (QoL) measures, the Bakas Caregiving Outcomes Scale, which was developed for use in stroke, will be adapted by replacing “stroke” with “traumatic brain injury” similar to a prior study.

The Bakas is a 15-item measure, each with a 7-point scale that assesses change in social functioning, emotional well-being, and physical health related to caregiving. It has been shown to have good internal consistency (Cronbach  $\alpha = 0.90$ ), test-retest reliability (intraclass correlation = 0.68), and construct validity. Following the recommendation from PCORI reviewers, we are currently exploring with our research team, including our patient and family stakeholders, other important caregiver domains (e.g., caregiver quality of life, role functioning and burden) as outcomes.

Zarit Burden Interview: The Zarit Burden Interview was initially developed for caregivers of individuals with dementia. Short forms have been developed, and the 12 item version addresses the concerns that our stakeholders feel are most important and that we feel are most relevant to our study interventions. The Zarit Burden Interview has been used previously in studies on caregivers of individuals with TBI. We hypothesize that caregivers for participants randomized into the RTP arm of the study will report lower burden compared to those caregivers of participants randomized into the RDP arm.

Prior research with this scale has been primarily descriptive and did not exactly match the timeline (within one year of TBI) nor injury severity of our study population. We can use the published data to estimate a possible standard deviation and given our expected sample size, we have 80% power to detect approximately a 2.29 difference if one exists. This is based on data from a study conducted on caregivers of Veterans with TBI who are broadly similar to our population with an average score of 15 and standard deviation of 10 on the 12 item Zarit Burden Interview. An assumption was made of equal sample sizes between the two groups which, with 80% power, alpha of .05, would require a .229 effect size to detect a difference between the two groups at 6 months post injury.

SF-12: The SF-12 is a measure of health-related quality of life (HRQOL) and allows for 2 component scores to be determined: physical health and mental health. The SF-12 has been used in examining HRQOL in caregiver populations for other disorders, but not as frequently assessed in caregivers of individuals with TBI. However, the 36-item version has been found to show change over time in caregivers of persons with TBI. We hypothesize that caregivers for participants enrolled in the RTP arm of the study will report better HRQOL in both physical and mental health domains compared to those caregivers of participants enrolled in RDP alone.

PROMIS Satisfaction with Social Roles and Activities: The PROMIS Satisfaction with Social Roles and Activities has not been used in the study of caregivers in any population to date. Given the other measures that we are including that specifically assess caregiver functioning and engagement in activities directly related to caregiving, we chose this measure to add an understanding of engagement in roles and activities apart from those related to caregiving. We hypothesize that caregivers for participants enrolled in the RTP arm of the study will report better satisfaction with social roles and activities compared to those caregivers of participants enrolled in RDP alone.

Required Assistance and Time Spent in Caregiving has been assessed in a variety of studies to describe the use of caregivers for individuals with TBI. This measure was developed internally with input from our Patient and Family Stakeholder group and experience from prior studies.

### **Assessment of Variability of Resources and Processes**

For RDP: During the preparation of our grant, we performed an assessment of the key resources and processes that are available at each of our inpatient rehabilitation sites, which include: (1) Patient and family education on diagnosis and anticipated needs, (2) written discharge instructions, (3) organization of outpatient services and appointments, (4) medication teaching and prescriptions, (5) discharge summary sent to primary care provider, and (6) post-discharge telephone call within a few days of discharge to reinforce discharge plan.

For RTP: We are aware that community resources will vary among our sites. Our patient and family stakeholders reported that the most important factors which contributed to them not getting their needs met following discharge from inpatient rehabilitation, were (1) lack of services to direct them to what resources were available or relevant to them and (2) limitations in insurance coverage (e.g., limiting availability of helpful services such as physical therapy, mental health treatment, etc.). Therefore, we will examine insurance coverage as a potential source of variability in outcomes. Moreover, during the start-up phase of the study, the TBI Care Manager (TCM) at each site will work closely with clinical and community stakeholders to familiarize themselves with all available resources at each site and across sites to increase the likelihood that all potential resources will be identified. Because the TCMs at all sites will be meeting via phone or videoconference on an ongoing basis, new resources that may be identified will also be shared to maximize awareness for all TCMs. We have agreement from our patient and family stakeholders and professional stakeholders to work with us to develop a list of key community resources across all sites, such as the availability of transportation, Department of Vocational Rehabilitation resources, support groups for patient and family, etc. that they feel may be relevant for individuals with TBI and their family/caregivers.

Also, during some sessions between the TCM and participant/ caregiver, the TCM will be using a checklist to determine needs as well as which patient-identified needs are met or unmet. If a need is unmet, we plan to document whether lack of available resources was the cause. While we cannot account for all variability in resources across the six sites/states, we will examine potential confounding and heterogeneity of treatment effects by study site and insurance coverage, which has significant influence on the resources available to patients. Finally, as described above, intervention fidelity will be closely monitored.

### **Power Analysis**

As can be seen in the Recruitment/Enrollment table above (p. 26), we expect to enroll a minimum of 300 individuals per year for 3 years (total N = 900). We based our power calculation on the PART-O-17, the primary outcome for which we have the most relevant data in TBI. Unpublished data from a sample discharged from inpatient TBI rehabilitation showed a PART-O-17 Total (which can range from 0 to 5) average score of 1.51 (SD=0.65) at 3-months follow-up and 1.66 (0.72) at 9-months follow-up (publication in preparation). Minimal detectable differences (MDD) were 0.57 and 0.63 at 3 and 9 months, respectively. Using these results, we calculated the power of finding a difference of 0.60 (average of the two MDDs) between the two groups under various assumptions as follows:

Test: t-test for independent samples, two-tailed, allocation ratio=1

[figure not shown]
Significance level=0.05

Common standard deviations: 0.75 (higher than the observed in previous studies to be conservative)

Mean PART-O scores (Intervention mean minus control mean): The minimal detectable difference of the instrument is 0.6. To be more conservative, we started the difference between the two means at 0.4. Assuming SD=0.75 (in the higher side of previous studies) the calculated effect size based on this mean and SD is 0.5333. Therefore, we used values of 0.5 to 0.8 by increments of 0.05 for the effect sizes.

[figure not shown]
Sample sizes: from 500 to 900 individuals (by 100)

The graph shows that even with an effect size of 0.5 (corresponding to a difference of 0.4 points between the two groups and under an SD larger than those observed in prior studies), we have practically 100% power to detect the difference between the two groups with sample sizes of 500 and above (we expect to have 900).

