The PART-O-17 was chosen for the current study because: (1) consumer stakeholders provided input into its development, (2) it is a patient-reported outcome, (3) it has established reliability and validity, and (4) our Patient and Family Stakeholders felt that it and the QoLIBRI captured the outcomes that were most important to them. The measure maintains the strengths and overcomes some of the weaknesses of its component measures. Persons with brain injury, family members, and advocates assisted in the development of the PART-O-17, helping to ensure that it captured key roles and activities important to persons with TBI and their families (including important domains of participation: productivity, social relations, and being out and about in the community), and contributing to the development of an abbreviated version (PART-O-17, original version had 24 items). Test-retest reliability is strong for both the total score and the domain scores (ICC=.90 for total score and ranges from .79 to .87 for the domain scores, personal communication, [name], manuscript under review). Construct validity has been demonstrated in TBI populations through principal component analysis suggesting that the PART-O measures a unidimensional construct, and through correlations of the expected strength and direction with legacy measures of participation, as well as with measures of injury severity, functional limitations, subjective well-being, and mental and physical health. In addition, the PART-O-17 was found to be sensitive to disability status in a population-based study.

A content analysis of the most frequently used participation measures (7 in total) indicated that the PART-O is the most representative of the ICF categories of participation. A recent rating scale analysis created a new scoring algorithm for the total score that reflects a unidimensional numeric measure. The PART-O 17 is a recommended outcome measure in the NIH Common Data Elements and has been used in the NIDILRR TBIMS National Dataset since 2007 ([https://commondataelements.ninds.nih.gov/tbi.aspx#tab=Data\\_Standards](https://commondataelements.ninds.nih.gov/tbi.aspx#tab=Data_Standards)).

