### **Data Analysis Plan Specific to Each Aim (IR-3, IR-5)**

**General approach:** The expected sample size is very large and we anticipate 100% power to find a difference in PART-O-17, if a difference exists. In addition, the sample size will allow us adequate power to examine our other aims and heterogeneity of treatment effects. We will use a significance level of 0.05 for all the analyses we will perform. Given the large sample size and the extremely high power for the primary outcome, we will not adjust the significance level for multiple comparisons for all the other tests, since it is highly likely that the p-values for those tests will be small. As it is well known and now stated in a publication by the American Statistical Association, the p-value should not be the single deciding measure of the significance of a result. Therefore, we will interpret the results of all non-primary outcomes with caution and will examine effect sizes as well as explicitly report the secondary outcomes status when presenting the results. We will obtain input from our stakeholders regarding the meaningfulness and importance of the effects.

The analysis plan will conform to the intent-to-treat principle: all randomized cases will be included based on their assigned treatment group regardless of actual intervention received. Missing values will be prevented and minimized by implementing the following steps in the manual of operations: 1) Prompt data entry to allow timely detection of any missing data, 2) Procedures for monitoring and tracking data completeness will be in the manual of operations, 3) When missing data are identified, research staff will contact the participant to collect them (if not time-contingent or outside the specified time range for collection). At the end of the study, participants not assessed at the end of intervention will be considered as having missing outcome values.

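### The PART-O-17 power claim takes a single-patient measurement-error limit as the between-arm target, and the unconditional power statements built on it are not correct

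*Combined protocol and SAP*

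**What the plan says.** The Power Analysis section reports, from an unpublished sample discharged from inpatient TBI rehabilitation, an "average score of 1.51 (SD=0.65) at 3-months follow-up and 1.66 (0.72) at 9-months follow-up". It adds: "Minimal detectable differences (MDD) were 0.57 and 0.63 at 3 and 9 months, respectively". It then takes their average as the difference between arms: "we calculated the power of finding a difference of 0.60 (average of the two MDDs) between the two groups". Calling 0.6 a property of the instrument, it continues: "To be more conservative, we started the difference between the two means at 0.4". With an SD of 0.75 this gives an effect size of 0.533. The section evaluates effect sizes from 0.5 to 0.8 and finds almost complete power from 500 participants upwards.

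The Primary Outcomes section gives the test-retest reliability of the PART-O-17: "ICC=.90 for total score and ranges from .79 to .87 for the domain scores".

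Power Analysis Revisited (January 2019) extends the effect sizes down to 0.3 without using the MDD. It gives 0.80 power for 300 participants at 0.3 and concludes that a real difference is unlikely to be missed.

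The general approach in Data Analysis Plan Specific to Each Aim then says "we anticipate 100% power to find a difference in PART-O-17, if a difference exists". It gives the very high primary-outcome power as a reason for not adjusting the other tests for multiple comparisons.

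**The concern.** An MDD for an instrument answers the question of how much one patient's score must change before the change exceeds measurement noise. A trial compares two arm means, in which that noise is averaged over hundreds of patients. The target there should be a difference that is plausible for the treatment, or important to patients. The MDD is neither: at a given reliability it is a fixed multiple of the SD whatever the treatment does. A value such as 0.4 is therefore not shown to be cautious by being smaller than 0.6. The section cites no earlier treatment effect and no between-group important difference for either figure.

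What is at stake is how the result is read. Power stated as 100% whenever a difference exists invites a reader to take a non-significant result as evidence of no effect. The same claim is also used to support the multiplicity decision.

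**Working it through.** **Inputs.** SDs 0.65 and 0.72, MDDs 0.57 and 0.63, planning SD 0.75: Power Analysis. ICC 0.90: Primary Outcomes. Design: "Test: t-test for independent samples, two-tailed, allocation ratio=1"; "Significance level=0.05". Analysed number: 900 enrolled with 80% retention (Table 1, Recruitment/Enrollment Assessment Timeline; Appendix 1 also counts 720 six-month follow-ups), so 0.80 × 900 = 720.

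**1. Where the MDD comes from.** The 95% limit for change in one patient is 1.96 × √2 × SD × √(1 − ICC).
- 3 months: 1.96 × 1.414 × 0.65 × √0.10 = 0.570 (stated 0.57).
- 9 months: 1.96 × 1.414 × 0.72 × √0.10 = 0.631 (stated 0.63).

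Both match to two decimals. The 90% version (1.645 in place of 1.96) gives 0.48 and 0.53, and an ICC of 0.91 gives 0.54 and 0.60; neither matches. With ICC 0.90 the limit is 1.96 × 1.414 × 0.316 = 0.88 SD.

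**2. The plan's own power figure.** (0.57 + 0.63)/2 = 0.60, and 0.4/0.75 = 0.533. At d = 0.5 and N = 500 the noncentrality is 0.5 × √(500/4) = 5.59 and the power is 0.9998. The figure reproduces. (At SD 0.75, d = 0.5 is 0.375 points rather than 0.4, a minor rounding.)

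**3. Power at smaller differences.** Noncentrality = (Δ/0.75) × √(N/4); two-sided 0.05; noncentral t.

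| Δ (points) | d | Power, N = 720 | Power, N = 900 |
|---|---|---|---|
| 0.10 | 0.13 | 43% | 51% |
| 0.15 | 0.20 | 76% | 85% |
| 0.20 | 0.27 | 95% | 98% |
| 0.225 | 0.30 | 98% | 99% |
| 0.40 | 0.53 | about 100% | about 100% |

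For scale only, the cited means differ by 1.66 − 1.51 = 0.15 points between months 3 and 9.

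**4. Detectable difference at N = 720.** (z₀.₉₇₅ + z_power) × 0.75 × √(4/720):
- 80% power: (1.960 + 0.842) × 0.0559 = 0.157 points (d = 0.21).
- 90% power: (1.960 + 1.282) × 0.0559 = 0.181 points (d = 0.24).
- 99% power: (1.960 + 2.326) × 0.0559 = 0.240 points.

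**5. The 2019 figure.** At N = 300 and d = 0.3 the noncentrality is 0.3 × √75 = 2.60. Two-sided power is 0.74, not 0.80 (one-sided it would be 0.83). The number needed for 80% is 4 × (2.802/0.3)² = 349, so about 350. The caregiver paragraph of the same 2019 section gives 350 for that effect size and power.

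**The case against.** The strongest case on the other side is that little depends on the MDD. The Power Analysis claim is conditional on an effect size of 0.5 and is right on that condition. The 2019 revisit works from 0.3 without the MDD, and at 720 analysed an effect of 0.3 has 98% power. The 900 is presented as a recruitment estimate, not as a number solved from 0.6 or 0.4. Version 15.0 is dated January 2023, after the scheduled end of recruitment and the primary completion date, so no design choice is open. All of this stands, and it limits the point to the basis of the effect size and to the statements that drop the condition. The revisit does not remove the point, because it justifies no effect size and ends on an unconditional conclusion of its own.

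Four stronger readings are tempting and not supported:
- **High power exists only near 0.4 points, 2.7 times the 0.15 rise in the cited means.** It does not: power is 95% at 0.20 and 99% at about 0.24.
- **The 0.15 bounds the treatment effect.** It is a change over time from month 3 to month 9 in one sample. It omits the first three months after discharge, when the intervention begins, and it is not a difference between arms.
- **The MDD will be used to dismiss a smaller observed difference.** No section makes it a threshold. The analysis plan takes stakeholder input on whether effects matter, and stakeholders are recorded as valuing any improvement.
- **The trial is too small.** The documents give no justified target against which to say so, and the detectable differences above are modest.

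**Conclusion.** The point holds as a fault in the effect-size basis and in the wording that follows from it. It is not an arithmetic error in the main power figure. The target of 0.60 is a single-patient quantity, and 0.4 is cautious only relative to it. The statements that power is 100% if a difference exists, and that a real difference is unlikely to be missed, describe a property the design does not have: at 720 analysed, power is 43% for 0.10 points and 76% for 0.15. The 2019 figure of 0.80 for 300 participants at 0.3 should be about 0.74.

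The conclusion rests on the planning SD of 0.75, 80% retention and the unadjusted two-sample t-test in the plan. With SD 0.72 the difference detectable at 80% power falls slightly, to 0.15 points. The reading of the MDD is an inference, since the Power Analysis does not state its formula, but both values follow from the protocol's own SDs and ICC. The consequence is moderate: the trial keeps good power for differences well below 0.4.

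**What to change.** **Power Analysis.** State that the MDD describes change in one patient, remove it as the target between arms, and delete the clause that presents 0.4 as the more cautious choice.

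**Power Analysis, Power Analysis Revisited and the general approach of the Data Analysis Plan.** Replace the unconditional power statements with: *with 720 analysed, two-sided 0.05 and SD 0.75, the trial has 80% power for 0.16 points (d = 0.21) and 90% power for 0.18 points.*

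**Power Analysis Revisited.** Correct 0.80 to about 0.74 for 300 participants at an effect size of 0.3. The 0.6 and 0.4 targets do not appear there, so nothing else about the MDD needs removing.

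**General approach.** Stop giving complete or very high power as the reason for not adjusting for multiple comparisons. If the decision stands, give it another reason.

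The cost is wording only. The sample size, test and analysis do not change, and the stated power becomes less favourable.

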### Power for Secondary Outcomes

For Aim 3, we consulted our stakeholders to determine what would represent meaningful differences in healthcare utilization. Based on these discussions, we will categorize completed planned outpatient visits in “less than 50%,” “between 50 and 75%,” and “more than 75%.” Based on highly conservative estimates from data collected on patients who were eligible (based on insurance, geography and preference) and referred to Moss Rehab Hospital (one of our study sites), 4%, 17%, and 79% of the individuals received “less than 50%,” “between 50 and 75%,” and “more than 75%” of their scheduled physical therapy, occupational therapy, and speech therapy care visits (these data do not include other outpatient visits, such as mental health and primary care visits, that are known to have low adherence rates). Under the assumptions that our RDP group would have a proportion of 0.79 of people going to more than 75% of their scheduled visits, with a significance level of 0.05, power of 0.80, and varying the sample size from 500 to 900, we calculated the size of change in the proportion of people receiving 75%+ visits in the RTP group that we would be able to detect. We would be able to statistically detect a proportion of 0.88 in the RTP group with a sample size of 500 and a proportion of 0.86 with 900 (see graph below). Therefore, we would have enough power to detect a small change in proportions.

[figure not shown]
We will also test differences in number of hospitalizations, number of emergency department visits, and number of unplanned outpatient visits per year. These outcomes will be compared using a Poisson model. For the power analysis, we adjusted the significance level to 0.017 after using Bonferroni adjustment (0.05/3), and we considered sample sizes of 700, 800, and 900 (to assess the effect of attrition of roughly 10% and 20%). From our previous work, we only have rough estimates of the events of interest (0.42 hospitalizations per year from [name] et al. and 2.25 medical encounters of any type (not distinguished as planned or unplanned) per year from Salisbury et al.). Therefore, we considered the base rates of 1-5 events per year for the RDP group and calculated the power of detecting a decrease in that rate of 10%, 20%, 30%, and 40% in the RTP group. Using G\*Power and the specifications above, the summary of the findings are as follows:

- The higher the base rate for the RDP group, the higher the power to find a difference;
- Power is at least 80% to find a decrease of 20% in the number of events, except when the base rate is 1, in which case the decrease would need to be 22-25% to be detected;
- Attrition (represented by sample sizes of 800 and 700) have an effect but might be important only for a small base rate (such as 1 visit/year);
- Power for secondary analysis will be high to find a decrease of 20% in mean number of events (equivalent to odds ratio of .8 when comparing the RTP to the RDP group), even when sample size is depleted by attrition.

[figure not shown]
The analyses will be repeated adjusting for other factors (age, sex, race/ethnicity, education, injury severity, for example), to explore the effect of those factors on the outcomes (we are not powering the study for these analyses as they are exploratory in nature).

The graphs below show the power for each base rate (odds ratio in x-axis and power in the y-axis).

[figure not shown]
